4.10. Differentiation Syndrome

Differentiation syndrome (DS) is a relatively common and potentially severe complication seen in patients with acute promyelocytic leukemia treated with all-trans retinoic acid and/or arsenic trioxide. The syndrome includes, but may not be limited to, unexplained fever, weight gain, dyspnea with pulmonary infiltrates, pleuro-pericardial effusion, hypotension, and/or renal failure. Cases of DS have been recently reported in patients with various types of AML administered FMS-like tyrosine kinase 3 (Flt3) inhibitors and isocitrate dehydrogenase (IDH) inhibitors.

Although the pathogenesis of DS has not been entirely clarified, it has been speculated it is due to a cascade of pathophysiologic mechanisms, leading to a systemic inflammatory response syndrome, endothelium damage with capillary leak syndrome, occlusion of microcirculation, and tissue infiltration with leukocytes. In this study, a diagnosis of DS should be suspected in subjects with AML in the presence of any of the above-mentioned signs and symptoms, and preemptive treatment with dexamethasone should be started immediately, particularly in patients with leukocyte counts greater than $10,000/\mu L$. Other supportive measures can also be crucial for

the correct management of DS, especially in patients with life-threatening complications (Sanz 2014). Temporary interruption of voruciclib is indicated for patients in poor clinical condition. Treatment with hydroxyurea (or an anthracycline if appropriate) to control rising leukocyte counts is also recommended.

Two subjects with AML enrolled in Cohort 2 (monotherapy) of this study experienced symptoms consistent with DS in Cycle 1 of voruciclib administration, including fever, hypoxemia, pulmonary infiltrate, and pleural effusion. The mechanism by which voruciclib may induce DS is unclear. Investigators should be aware of DS as differential diagnosis in patients with AML experiencing fever, pulmonary or hemodynamic complications in the first weeks of voruciclib administration. After ruling out an infection or other causes, treatment with dexamethasone and supportive care measures is recommended. Hydroxyurea (1-2 g/day) or an anthracycline (if appropriate) can be used to control rising leukocyte counts.

4.11. Interstitial Lung Disease/Pneumonitis

Interstitial lung disease (ILD)/pneumonitis has been reported post-marketing with the CDK4/6 inhibitors, which are approved in the US for the treatment of patients with breast cancer (FDA Drug Safety Communications, September 2019). With the continuous dosing schedule of voruciclib, 2 subjects with AML had DLTs of pneumonitis (n = 1) or ILD (n = 1) at the 100 mg QD dose level. Of note, the 2 subjects had confounding factors that may have contributed to this toxicity, including a history of secondary AML following a myelodysplastic syndrome, heavily pretreated disease, allogeneic stem cell transplantation in the preceding 12 months, and evidence of differentiation syndrome occurring 1 to 2 weeks after voruciclib initiation. These DLTs prompted the Sponsor decision to no longer pursue a QD dosing schedule in either disease group. In addition, one subject with DLBCL enrolled at the 50 mg QD dose cohort experienced hypoxemic respiratory failure with pulmonary infiltrates in Cycle 4. There was no identified cause for this event, which was considered related to study drug and led to voruciclib discontinuation.

The mechanism of this pulmonary toxicity is not understood. PK data from the Phase 1 studies in solid tumors indicated that voruciclib has a very high volume of distribution (>100 L), suggesting higher exposure in tissues than in plasma.

Subjects should be monitored for symptoms indicative of ILD/pneumonitis (e.g., hypoxia, cough, dyspnea), with management as indicated in Table 12. In subjects with new or worsening respiratory symptoms and in whom pneumonitis is suspected, voruciclib administration is to be suspended and permanently discontinued if pneumonitis is confirmed.

Table 12: Monitoring and Management of Interstitial Lung Disease/Pneumonitis

Grade 1	Monitor patients weekly with history and physical examination, pulse oximetry and imaging
Grade 2	Hold voruciclib until at least \leq Grade 1 Consider prednisone 1-2 mg/kg/day with taper by 5-10 mg/week over 4-6 weeks Consider bronchoscopy with bronchoalveolar lavage (BAL) Consider empiric antibiotics Monitor Q3 days with history and physical examination, pulse oximetry and imaging

Grade 3 or 4	Permanently discontinue voruciclib Consider empiric antibiotics Consider methylprednisolone IV 1-2 mg/kg/day Consider infliximab 5 mg/kg or mycophenolate mofetil IV 1 gm twice daily or IVIG X 5 days or cyclophosphamide if no improvement Consider pulmonary and infectious disease consults Patients should be hospitalized for further management
--------------	---

Adapted from [Brahmer 2018](#).

4.12. Subject Replacement

Subjects who discontinue study therapy prior to completing Cycle 1 (Day 28) for reasons other than the development of a DLT will be replaced. Subjects who miss one or more doses for reasons other than DLT, must receive at least 75% of the total planned voruciclib dose in Cycle 1 to be assessed for DLT. Subjects with no DLT who fail to receive at least 75% of the planned Cycle 1 voruciclib dose will be replaced.

For Cohort 12, subjects must receive 100% of Cycle 1 doses (i.e., all 6 doses) to be DLT evaluable; subjects with no DLT who fail to receive 100% of Cycle 1 voruciclib doses will be replaced.

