In Amendment 11, subsequent to determination of the safe and mBED of voruciclib monotherapy in AML subjects, the combination of voruciclib with venetoclax will be evaluated in subjects with relapsed and/or refractory AML (see rationale provided below).

The combination cohorts, beginning at Cohort 12 dose level of voruciclib in combination with venetoclax on an IS_{2w,2w} dosing schedule, will be enrolled as follows:

- Cohort 12: 50 mg once every other day (QOD), administered IS_{2w,2w} + venetoclax administered QD × 28 days
- Cohort 13: 50 mg QD, administered IS_{2w,2w} + venetoclax administered QD × 28 days
- Cohort 14: 100 mg QD, administered IS_{2w,2w} + venetoclax administered QD × 28 days
- Cohort 15: 150 mg QD, administered IS_{2w,2w} + venetoclax administered QD × 28 days
- Cohort 16: 200 mg QD, administered IS_{2w,2w} + venetoclax administered QD × 28 days
- Cohort 17: 250 mg QD, administered IS_{2w,2w} + venetoclax administered QD × 28 days
- Cohort 18: 300 mg QD, administered IS_{2w,2w} + venetoclax administered QD × 28 days
- Cohort 19: 350 mg QD, administered IS_{2w,2w} + venetoclax administered QD × 28 days

Dose escalation to the next cohort will be reviewed by the SRC after 3 subjects have completed 1 cycle with no reported DLTs, or after 6 subjects have completed 1 cycle with no more than 1 DLT. (DLT criteria defined below.) Escalation to a subsequent cohort will depend on demonstrated safety and tolerability within a cohort and with the approval of the SRC.

If the next dose level in the AML combination cohort has been declared safe by the SRC, subjects enrolled at a lower dose level may have their dose escalated to the next dose level after completing Cycle 1 without a DLT (intra-subject dose escalation). For example, a subject with AML enrolled in Cohort 13 (50 mg IS_{2w,2w}) may have the dose increased to 100 mg in Cycle 2 if the dose of 100 mg IS_{2w,2w} was deemed safe in Cohort 14 by the SRC.

Dose escalation proceeds until a real-time assessment of clinical and PK parameters by the SRC establishes the safe and mBED for voruciclib in combination with venetoclax. More specifically, a voruciclib dose in combination with venetoclax that meets the following criteria:

- DLT not to exceed 1 in 6 subjects, overall response rate (ORR) ≥30%, as compared to historical ORR of 19% with 400-800 mg venetoclax alone in relapsed/refractory AML ([Konopleva 2016](#)), and

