For the combination cohorts on IS_{2w,2w} (Amendment 11), the starting dose of voruciclib in Cohort 12 is 50 mg QOD, which will further reduce voruciclib exposure to account for potential increases (if any) in bioavailability of the new malonate tablet formulation during the exposure cycles. Dosing in Cohort 13 (50 mg QD) will commence only after the safety of QOD dosing of voruciclib with venetoclax in Cohort 12 is established.

For the first two dose levels (50 mg QOD and 50 mg QD), for which voruciclib dose reduction is not possible, voruciclib will be temporarily stopped if the subject requires treatment with an azole antifungal due to the potential of drug-drug interactions and increase exposure to voruciclib. Subjects who recover from the infection can restart voruciclib after the last dose of the azole antifungal (after at least 5 times the half-life of the agent). For subjects receiving

voruciclib at or above 100 mg, a dose reduction by 1 dose level will be required for concomitant treatment with an azole or other strong CYP3A4 inhibitor.

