### **6.2 DLT Evaluable Set**

The DLT Evaluable Set will comprise all subjects in the Safety Evaluable Set who completed the first cycle of treatment (defined as taking at least 75% of the prescribed dose during Cycle 1; for Cohort 12, subjects must receive 100% of Cycle 1 doses (i.e., all 6 doses)) or experienced a DLT during the first cycle of treatment. Subjects who discontinue study therapy prior to completing Cycle 1 (Day 28) for reasons other than the development of a DLT will be replaced. Also, subjects with no DLT who fail to take at least 75% of the planned Cycle 1 voruciclib dose will be replaced; for Cohort 12, subjects with no DLT who fail to receive 100% of Cycle 1 voruciclib doses will be replaced.

The DLT rate will be computed based on subjects in the DLT Evaluable Set.

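### The 75% rule for DLT evaluability does not require doses at the assigned level, so a subject on a reduced voruciclib dose can count as DLT-free at the cohort dose

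*Protocol*

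**What the plan says.** Protocol Section 4.12 says that subjects who miss doses for reasons other than DLT "must receive at least 75% of the total planned voruciclib dose in Cycle 1 to be assessed for DLT". It continues: "Subjects with no DLT who fail to receive at least 75% of the planned Cycle 1 voruciclib dose will be replaced". Cohort 12 alone is ruled by a count: "subjects must receive 100% of Cycle 1 doses (i.e., all 6 doses) to be DLT evaluable".

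The other definitions use different terms:

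- Protocol 10.3 and 10.3.2 ask for 75% study drug compliance.
- SAP 3.1.4 refers to the planned dose.
- SAP 6.2 treats a completed first cycle as "defined as taking at least 75% of the prescribed dose during Cycle 1", yet its replacement sentence goes back to the planned dose.

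None of these states the dose level at which the 75% must be taken. SAP 7.6 reports dose-modified subjects at their initial level. Protocol 4.3.1.1 and SAP 3.1.1 keep subjects whose dose was raised out of the DLT count at the higher level, but there is no matching rule for subjects whose dose was lowered.

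A one-level reduction is written into Protocol 4.15: for subjects on "voruciclib at or above 100 mg, a dose reduction by 1 dose level will be required for concomitant treatment with an azole" or another strong CYP3A4 inhibitor. No exception is made for Cycle 1. Section 4.14.1 instead has voruciclib held while an azole is given.

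**The concern.** A 3+3 decision rests on three or six subjects, each taken as an observation of the cohort dose. The evaluability rule should make sure of that. Here it is a share of dose, while the levels sit a fixed 50 mg apart. As the cohort dose rises, the level below becomes a larger share of it and eventually reaches 75%. From there on, a subject can satisfy the rule without one dose at the level being tested. Subjects with the same reduction are then evaluable in some cohorts and replaced in others, with no reason given for the difference.

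At stake is what stands behind an escalation or a safe-dose declaration. One off-level subject is a third of the evidence in a cohort of three, and the strong inhibitor that prompted the reduction would itself have altered that subject's voruciclib exposure.

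**Working it through.** **Planned Cycle 1 doses.** Cohort 12 takes voruciclib on Days 3, 5, 7, 9, 11 and 13, which is 6 doses and reproduces the count in Section 4.12. From Protocol 4.3.2.1, combination IS2w,2w covers Days 3 to 14 (14 − 3 + 1 = 12 doses) and IS3w,1w covers Days 3 to 21 (21 − 3 + 1 = 19 doses).

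**Dose levels.** Tables 3 and 4 and the synopsis give 50 mg steps, for example "Cohort 15: 150 mg QD", "Cohort 16: 200 mg QD" and "Cohort 17: 250 mg QD", up to 350 mg.

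**Whole cycle one level down.** Share of planned mg = (d − 50)/d, whatever the number of doses. The last column gives the doses that could also be missed with the share still at 75% or more.

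| Cohort dose (mg) | Cohorts | Share | At least 75%? | Further misses allowed (of 12; of 19) |
|---|---|---|---|---|
| 100 | 14 | 50/100 = 50.0% | no | – |
| 150 | 15, 21 | 100/150 = 66.7% | no | – |
| 200 | 16, 22 | 150/200 = 75.0% | yes, exactly | 0; 0 |
| 250 | 17, 23 | 200/250 = 80.0% | yes | 0; 1 |
| 300 | 18, 24 | 250/300 = 83.3% | yes | 1; 1 |
| 350 | 19, 25 | 300/350 = 85.7% | yes | 1; 2 |

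At 200 mg, one missed dose gives (11 × 150)/(12 × 200) = 68.75%, a fail. Two levels down always fails; the highest share is 250/350 = 71.4%.

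**Part of the cycle one level down.** This qualifies below 200 mg too. At 150 mg:

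- 9 of 12 doses at 100 mg: (3 × 150 + 9 × 100)/1,800 = 1,350/1,800 = 75.0%.
- 14 of 19 doses at 100 mg: (5 × 150 + 14 × 100)/2,850 = 2,150/2,850 = 75.4%.

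**Other readings of the 75%.** If the denominator is the reduced prescription, or if doses are counted whatever their strength, a fully compliant reduced subject scores 100% in every cohort.

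**Effect on a 3+3 decision.** Pass probability = P(0 DLTs in first 3) + P(1 in first 3) × P(0 in next 3). The documents give no DLT rates, so those below are assumptions. One of the first three subjects is reduced; all others have a 35% risk, so P(0 in next 3) = 0.65³ = 0.2746.

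| Risk in the reduced subject | P(0 of 3) | P(1 of 3) | Pass probability |
|---|---|---|---|
| 15% | 0.85 × 0.65² = 0.3591 | 0.4501 | 0.3591 + 0.4501 × 0.2746 = 0.48 |
| 35% (no difference) | 0.65³ = 0.2746 | 0.4436 | 0.2746 + 0.4436 × 0.2746 = 0.40 |
| 45% | 0.55 × 0.65² = 0.2324 | 0.4404 | 0.2324 + 0.4404 × 0.2746 = 0.35 |

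**The case against.** The strongest reply is that the whole-cycle case is nearly closed off:

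- Exclusion 7c has strong or moderate CYP3A inhibitors stopped at least 3 days before venetoclax, and voruciclib starts only on Day 3.
- Section 4.14.3 requires a washout of prohibited drugs such as azoles before Day 1.
- Section 4.14.1 excludes azoles from antifungal prophylaxis in the combination cohorts.
- If voruciclib is held with an azole, as 4.14.1 says, the held doses are missed doses and the 75% rule works as intended.
- Tables 10 and 11 set out no toxicity-driven one-level reduction within Cycle 1 for a DLT-free subject.

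This stands as a limit on frequency. A reader might infer that subjects will routinely spend Cycle 1 one level down; the documents do not support that. They do not rule it out either. Table 13 gives AML ramp-up doses of venetoclax with strong inhibitors, Section 9.14.2 plans a PK comparison with and without azoles, and Section 4.15 also covers strong inhibitors other than azoles.

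A second reply is that the break at 200 mg depends on counting in mg. That is right: the compliance and prescribed-dose wordings can be read otherwise. Those readings remove the break but admit the compliant reduced subject everywhere, so the missing dose-level condition remains.

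Third, the Study Review Committee sees safety, PK and PD data and must approve escalation (Protocol 4.3.2, SAP 7.10), so an off-level subject could be noticed. This lowers the risk, but no text tells the committee to set such a subject aside.

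Finally, Cohorts 16 and 17 were already past at Amendment 12, with no DLTs reported through 250 mg on IS2w,2w and 300 mg enrolling. The point therefore bears mainly on Cohorts 18, 19 and 21 to 25.

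**Conclusion.** The gap is real: as written, a DLT-free subject who took some or all Cycle 1 doses one level down can be evaluable at the cohort dose. In mg, the whole-cycle version qualifies at 200 mg and above (at 200 mg only with no missed dose), and partial reductions qualify below that. The ratios are exact and rest only on the stated levels.

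A reader might go further and infer that the rule makes high doses look safer than they are. The documents do not support a direction. The reduction in Section 4.15 accompanies a strong CYP3A4 inhibitor, Section 4.14.1 calls voruciclib a CYP3A4 substrate, and Section 4.15 expects azoles to raise its exposure. A lower mg dose need not mean lower exposure or lower DLT risk. Under the assumed rates, one reduced subject in the first three moves the pass probability from 0.40 to anywhere between 0.35 and 0.48, including no change. What can be said is that such a subject does not observe the dose under test. The change is worth making while cohorts are open, but whole-cycle reduction should be regarded as an extreme case.

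**What to change.** In Protocol 4.12, 10.3 and 10.3.2 and SAP 3.1.4 and 6.2, use one definition: a DLT-free subject is evaluable if at least 75% of the planned number of Cycle 1 voruciclib doses were taken at the assigned dose level. On combination IS2w,2w this is 0.75 × 12 = 9 doses; on IS3w,1w it is 0.75 × 19 = 14.25, so 15. Keep the Cohort 12 rule of all 6 doses. State that a DLT in a reduced subject still counts as an event, and that a DLT-free subject below the threshold is listed and replaced for the escalation decision.

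A subject one level down throughout then scores 0 of 12 or 0 of 19, so every adjacent pair of levels is separated. Raising the mg threshold would serve less well. It would have to exceed 85.7%, which leaves room for only 1 missed full dose of 12 (11/12 = 91.7%, 10/12 = 83.3%) or 2 of 19 (17/19 = 89.5%, 16/19 = 84.2%).

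Separately, Sections 4.14.1 and 4.15 must be reconciled on voruciclib during azole treatment; the evaluability wording does not depend on how that is settled. The cost is text in both documents and an occasional extra replacement subject in a cohort.

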4.4. Dose-Limiting Toxicity (DLT)

A DLT will be defined as any of the following treatment-emergent adverse events (TEAEs) occurring in Cycle 1 of voruciclib monotherapy or voruciclib + venetoclax combination therapy that are clearly unrelated to the underlying disease or extraneous causes:

- Symptomatic nonhematological Grade ≥ 3 laboratory abnormalities or asymptomatic nonhematological Grade ≥ 3 laboratory abnormalities that fail to improve to Grade ≤ 2 within 72 hours
- Grade 3 vomiting lasting >48 hours despite recommended antiemetic support or any occurrence of Grade ≥ 4 vomiting
- Grade 3 diarrhea lasting >48 hours despite recommended antidiarrheal support or any occurrence of Grade ≥ 4 diarrhea
- All other Grade ≥ 3 nonhematological adverse event (AE) not listed above
- Grade 3 or higher TLS regardless of prophylaxis
- Hy's law cases
- Febrile neutropenia of any duration (not applicable to AML subjects)
- Grade 4 neutropenia lasting ≥ 7 days; or lasting ≥ 42 days and not due to progressive disease in AML subjects
- Grade ≥ 3 thrombocytopenia with Grade ≥ 2 bleeding or Grade 4 thrombocytopenia of any duration (not applicable to AML subjects)
- Grade 4 thrombocytopenia lasting ≥ 42 days (AML subjects only)
- Grade 4 anemia unexplained by underlying disease

Hy's law cases of drug-related hepatocellular injury are defined as elevated ALT or AST $\geq 3 \times$ ULN, elevated total bilirubin $>2 \times$ ULN without findings of cholestasis, and no other reason can be found to explain the combination of increased aminotransferase and serum total bilirubin, such as viral hepatitis, alcohol abuse, ischemia, pre-existing liver disease, or another drug capable of causing the observed injury.

Additionally, discontinuation of study drug in Cycle 1 due to an AE that is clearly unrelated to the underlying disease, or an extraneous cause will be considered a DLT.

Safety will be assessed by AEs graded according to National Cancer Institute Common Terminology Criteria for Adverse Events (NCI CTCAE) v5.0; laboratory safety tests including hematology (complete blood count [CBC]), serum chemistry; physical examination; vital signs; ECOG performance status; and 12-lead electrocardiogram (ECG).

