Grade 3-4 neutropenia with or without fever or infection; or Grade 4 thrombocytopenia	
Prior to achieving a remission:
 
 Continue venetoclax unless treatment interruption is deemed necessary by the Investigator A bone marrow evaluation is recommended 
For subjects who achieve CR, CRh, or CRi, at the end of Cycle 1 (or later cycle):
 
 Hold venetoclax until recovery to Grade ≤ 2 Monitor blood counts Upon resolution to Grade 1 or 2, resume at the same dose 
Cycle 2 and beyond:
 
For subsequent occurrences in cycles after achieving remission and lasting ≥ 7 days, the following stepwise schedule duration reductions are allowed for persistent cytopenia:
 
 Hold venetoclax until recovery to Grade ≤ 2 Monitor blood counts. 
Retreat at same dose level and same schedule (no reduction)
	
Prior to achieving a remission:
 
 Continue voruciclib unless treatment interruption is deemed necessary by the Investigator A bone marrow evaluation is recommended 
For subjects who achieve CR, CRh, or CRi, at the end of Cycle 1 (or later cycle)
 
 Hold voruciclib until recovery to Grade ≤ 2 Monitor blood counts Re-treatment at the same dose and schedule is allowed If no recovery by Day 42 after start of Grade 4 neutropenia, retreat at one dose level lower and same schedule 
Cycle 2 and beyond:
 
 Hold voruciclib until recovery to Grade ≤ 2 Monitor blood counts. Retreat at one dose level lower and same schedule.

Adverse Reaction	Venetoclax	Voruciclib
	Reduction level 1: venetoclax duration may be reduced to administration on Days 1 through 21 of the 28-day cycle Reduction level 2: venetoclax duration may be reduced to administration Days 1 through 14 of the 28-day cycle	
Nonhematologic Adverse Reactions		
Grade 3 or 4 nonhematologic toxicities	Interrupt venetoclax if not resolved with supportive care. Upon resolution to Grade 1 or baseline level, resume venetoclax at the same dose.	See Requirement for Holding Dose or Discontinuing Study Drug and Retreatment with Voruciclib rules for non-hematologic toxicities in Table 10

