10. STATISTICS

10.1. Number of Subjects

At the start of Amendment 12, a total of 40 subjects have been enrolled in the now-completed monotherapy dose escalation/expansion cohorts. Assuming an average enrollment of 4 subjects per dose level for DLT evaluation, up to 12 subjects to be enrolled in the 2 combination AML expansion cohorts, and an additional 10% for early drop-outs due to non-evaluability after failure to complete Cycle 1 treatment for reasons other than AEs related to voruciclib, the total enrollment for the voruciclib plus venetoclax combination group is estimated to be approximately 68 subjects, for a total of approximately 108 subjects to be enrolled in the study.

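### Subjects whose study-drug toxicity falls short of a DLT but costs more than 25% of Cycle 1 voruciclib are replaced, so they enter the 3+3 neither as events nor in the denominator

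*Protocol*

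**What the plan says.** **Replacement.** Protocol 4.12 applies the first-cycle 75% rule to every cause except a DLT: "Subjects who miss one or more doses for reasons other than DLT, must receive at least 75% of the total planned voruciclib dose". It then adds: "Subjects with no DLT who fail to receive at least 75% of the planned Cycle 1 voruciclib dose will be replaced". SAP 6.2 agrees: "subjects with no DLT who fail to take at least 75% of the planned Cycle 1 voruciclib dose will be replaced". SAP 3.1.4 carries the same rule, and Protocol 10.3.2 defines the DLT evaluable population by 75% compliance or a DLT. For Cohort 12, Protocol 4.12 and the SAP are stricter: "subjects must receive 100% of Cycle 1 doses (i.e., all 6 doses) to be DLT evaluable".

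**What counts as a DLT.** Section 4.4 lists the criteria and adds "discontinuation of study drug in Cycle 1 due to an AE", provided the AE is clearly unrelated to the underlying disease or an extraneous cause. It has no item for interruption or missed doses.

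**Holds foreseen short of a DLT.**
- Table 12 (Section 4.11), Grade 2 pneumonitis: "Hold voruciclib until at least" Grade 1. The text above that table instead requires permanent discontinuation once pneumonitis is confirmed.
- Table 11 (Section 4.8.3), AML cytopenia before remission: "Continue voruciclib unless treatment interruption is deemed necessary by the Investigator". In AML, Grade 4 neutropenia or thrombocytopenia is a DLT only from 42 days, and febrile neutropenia is exempt.

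**How loss is described elsewhere.** Section 10.1 allows 10% for "non-evaluability after failure to complete Cycle 1 treatment for reasons other than AEs related to voruciclib". Section 4.1 and the note to Figure 1 (Section 4.3.1.1) justify the optional fourth subject by loss that has nothing to do with voruciclib toxicity.

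**SRC review.** Protocol 4.3.1.1 and SAP 7.10 make escalation conditional on review of subjects evaluable for DLTs. Protocol 4.3.2 says combination decisions are guided by all available safety data.

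**The concern.** Replacement is harmless to a 3+3 when the reason for loss is independent of toxicity. Here it need not be. A subject who cannot take the schedule because of a study-drug AE below the DLT threshold is removed, and another is enrolled until three or six evaluable subjects exist. The tally then describes DLTs among subjects who either had a DLT or took at least 75% of their doses. It says nothing about those who could not reach 75% because of lesser toxicity.

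Whether a toxicity is counted can also turn on an operational choice. If the investigator stops the drug, 4.4 makes it a DLT; if the investigator holds it for long enough, 4.12 removes the subject. Grade 2 pneumonitis shows this most clearly, because the 4.11 text leads to the first outcome and Table 12 to the second. The protocol gives pulmonary DLTs as the reason for abandoning continuous dosing, so this category matters to the trial.

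At stake are the escalation decision and the safety half of the mBED criterion (no more than 1 DLT in 6).

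**Working it through.** **1. How many missed doses trigger replacement.** Planned Cycle 1 doses come from Sections 4.3.2.1 and 5.1.

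| Schedule | Planned | Needed for 75% | Replaced if missed |
|---|---|---|---|
| Combination IS2w,2w (Days 3–14) | 12 | 9 | 4 or more |
| Combination IS3w,1w (Days 3–21) | 19 | 14.25, so 15 | 5 or more |
| Cohort 12 | 6 | 6 (100% rule) | 1 or more |
| Monotherapy IS2w,2w | 14 | 10.5, so 11 | 4 or more |
| Monotherapy IS1w,3w | 7 | 5.25, so 6 | 2 or more |

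**2. The plan's only related figure.** Section 10.1 gives about 68 combination subjects, including 10% for non-evaluability. There are 8 + 5 = 13 dose levels, and 13 × 4 = 52. Then 52 × 1.10 + 12 = 69.2, which is close to 68. That 10% is described as loss not caused by voruciclib-related AEs, so it says nothing about toxicity-driven under-dosing. No other figure in the documents does.

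**3. Model.** Let d be the probability of a DLT and m the probability of study-drug toxicity that is not a DLT but takes the subject below 75%. Both are assumptions. The design escalates on 0/3 or at most 1/6 (Section 4.3.2), so for an event rate p among counted subjects:

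P(clear) = (1 − p)³ + 3p(1 − p)⁵

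This ignores the optional fourth subject and the SRC's discretion. At the design's target DLT rate of 20–25% (Section 10.3) it gives 0.71 and 0.60. Three treatments of the under-dosed subjects are compared:
- replaced, as written: p = d/(1 − m)
- counted as events: p = d + m
- kept as evaluable without a DLT: p = d

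**4. One case in full (d = 0.15, m = 0.20).**
- Replaced: p = 0.15/0.80 = 0.1875; 0.8125³ + 3(0.1875)(0.8125⁵) = 0.536 + 0.199 = 0.74
- Counted: p = 0.35; 0.65³ + 3(0.35)(0.65⁵) = 0.275 + 0.122 = 0.40
- Kept: p = 0.15; 0.85³ + 3(0.15)(0.85⁵) = 0.614 + 0.200 = 0.81

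**5. Range.**

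| d | m | Replaced (as written) | Counted as events | Kept as non-DLT | At least one of first three replaced, 1 − (1 − m)³ |
|---|---|---|---|---|---|
| 0.05 | 0.05 | 0.97 | 0.91 | 0.97 | 14% |
| 0.10 | 0.10 | 0.89 | 0.71 | 0.91 | 27% |
| 0.15 | 0.20 | 0.74 | 0.40 | 0.81 | 49% |

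A simulation of 200,000 cohorts per treatment at d = 0.10, m = 0.30 gave 0.829, 0.310 and 0.906 for replaced, counted and kept. The formulas give 0.828, 0.309 and 0.906.

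**The case against.** The strongest reply is that the gap is narrow. Most Grade 3 or higher nonhematologic AEs are DLTs whatever dose was received, and so is AE-driven discontinuation clearly unrelated to disease or an extraneous cause. A reader might infer that doses are cleared on tolerant subjects only. The documents do not support that: a cleared cohort of six may contain a DLT, the SRC must approve escalation, and replaced subjects stay in the analysis sets they qualify for (SAP 3.1.4).

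Some tempting examples are weak:
- **Grade 3 vomiting or diarrhea of 48 hours or less.** Table 10 requires interruption only if it is not controlled within 48 hours. That span is about two daily doses, short of 4 of 12 or 5 of 19.
- **AML cytopenia.** Before remission a hold is the investigator's choice, not the default.
- **Grade 2 pneumonitis.** This is unsettled, because the 4.11 text and Table 12 point to different outcomes.

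A reader might also infer that Section 10.1 directly contradicts 4.12. It does not: 10.1 is a sample-size allowance, not a replacement rule. With Section 4.1 and the Figure 1 note, it shows only that the protocol thinks of non-evaluable loss as unrelated to the drug, a limit that 4.12 never imposes.

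Finally, the larger gaps in clearing probability arise only if every such subject is counted as an event. Against keeping them as non-DLT completers, replacement is the more conservative choice, because it raises the evaluable DLT rate (0.15 to 0.1875 above).

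All of this stands and limits the size of the point. It does not close the gap. No passage classifies a toxicity-caused hold, and none requires that replaced subjects and their reasons be shown to the SRC. SAP 7.10 ties the pre-escalation review to DLT-evaluable subjects, although it also has the SRC evaluate accumulating safety data.

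**Conclusion.** The point holds in this form. Study-drug toxicity that is not a DLT but costs more than 25% of Cycle 1 voruciclib (any one dose in Cohort 12) leaves the subject outside the 3+3 altogether, and the stop-or-hold choice can decide whether it is counted. This sits badly with the protocol's own description of non-evaluable loss, and the conflict within 4.11 leaves Grade 2 pneumonitis unclassified.

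The size is unknown. Over the assumed rates, the difference in clearing probability between the written rule and counting these subjects runs from 0.06 (0.97 versus 0.91) to 0.34 (0.74 versus 0.40). Those are bounds under stated assumptions, not an estimate of bias in this trial. The documents report no DLTs from 50 mg QOD to 250 mg QD on IS2w,2w and do not say how many subjects, if any, were replaced or why. A reader might infer that those cohorts were wrongly cleared; nothing in the documents shows that. Nor do they settle that every under-dosed subject should be a DLT, which is a clinical decision for the sponsor. The statistical requirement is that the classification be fixed before the data are seen.

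**What to change.** 1. In Protocol 4.12 and 10.3.2 and SAP 3.1.4 and 6.2, limit replacement to missed doses not caused by study-drug-related AEs.
2. Reconcile 4.4, the 4.11 text with Table 12, and 4.12, so that the place of toxicity-caused under-dosing in the 3+3 is fixed in advance. The sponsor decides the clinical criterion. These subjects should not simply become non-DLT completers, which would be laxer than the present rule.
3. Amend SAP 7.10 so that the SRC reviews all treated subjects before escalation. Give it a by-cohort listing of every replaced subject with the reason, and the 3+3 tally with and without toxicity-caused under-dosing counted as events.

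The cost is wording in both documents and one listing. SAP 8.5 already tabulates missed doses and reasons for dose modification, so most of the data should be in hand; check that the reason for each missed dose is captured. The downside is that some cohorts may expand to 6 or stop earlier than under the present rule.
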